14. STATISTICS

14.1. Determination of Sample Size

14.1.1. Dose Escalation Stage (Stage 1)

The planned sample size for the dose-escalation is not based on a specific statistical hypothesis but on experience in the conduct of similar trials in subjects with cancer.

In the dose escalation, the cohort sizes of 3 to 6 subjects allow evaluation of regimen safety using a standard definition of MTD (ie, a starting dose associated with DLT in <33% of subjects during the first cycle of therapy). Based on the planned 3+3 dose-escalation scheme, Table 14 shows the probability of escalating to the next dose level or proceeding to the next stage, based on the true rate of DLT at the current dose level.

Table 14: Statistical Basis for 3+3 Dose-Escalation Paradigm

True Incidence of DLT	Probability of Escalating
10%	0.91
20%	0.71
30%	0.49
40%	0.31
50%	0.17
60%	0.08

Abbreviation: DLT=dose-limiting toxicity

Thus, if the true underlying proportion of DLT is low (eg, $\leq 10\%$ at the current dose level, there is a high probability (≥ 0.91) of dose escalation to the next dose level. Conversely, if the true underlying proportion of DLT is high (eg, $\geq 60\%$) at the current dose level, there is a low probability (≤ 0.08) of escalation to the next dose level.

14.1.2. Cohort Expansion Stage (Stage 2)

As indicated in Section 6.1.2, expansion cohorts of 6 subjects will be accrued. Enrollment of 6 subjects per cohort offers the opportunity to determine if there is any antitumor activity sufficient to warrant further development in the selected tumor types. An ORR of \geq 35% is considered of potential interest in each of the selected indications. If 0/6 subjects in a cohort experience an objective response, then a population ORR of \geq 35% for that cancer can be excluded with > 90% certainty (1-sided exact binomial 90% CI upper bound = 32%).

Based on the observation of objective responses among study subjects with FL receiving either LAM-002A monotherapy or LAM-002A/rituximab, expanded accrual of subjects with relapsed FL is planned to evaluate the level of activity with these 2 regimens. Preference will be given to enrolling subjects to receive LAM-002A monotherapy before enrolling subjects to receive LAM-002A/rituximab.

Based on historical data with other treatments (Zelenetz 2014), it is known that an ORR of < 20% in subjects with relapsed FL receiving LAM-002A monotherapy would be uninteresting while achieving a target ORR of $\ge 40\%$ would suggest that further development is warranted. Sequential boundaries will be used to continuously monitor that the ORR is $\ge 40\%$ while

Version 9, 18 Feb 2020

excluding an ORR of < 20% using a 1-sided test with a significance level of 0.05. A significant result with this testing would conclude with 95% confidence that the actual ORR is \geq 20%. Accrual of up to ~20 evaluable subjects will be considered with the potential to stop accrual early if the boundary is crossed. Thus, accrual can be considered sufficient if the following n/N values are observed: 4/5, 4/6, 4/7, 5/8, 5/9, 5/10, 5/11, 6/11, 6/12, 6/13, 6/14, 7/15, 7/16, 7/17, 8/18, 8/19, 8/20. For all these values, the ORR is \geq 40% with a lower 1-sided binomial confidence bound of \geq 20%.

As noted above, the target ORR with LAM-002A alone is ~40%. Adding rituximab or rituximab hyaluronidase human to LAM-002A would be expected to enhance the ORR over that associated with single-agent LAM-002A. Thus, the combination of LAM-002A/rituximab could warrant further development if an ORR of \geq 60% could be targeted in preference to an ORR of < 40%. Accordingly, for combination therapy, sequential boundaries will be used to continuously monitor that the ORR is \geq 60% while excluding an ORR of 39% using a 1-sided test with a significance level of 0.05. A significant result with this testing would conclude with 95% confidence that the actual ORR is > 39%. Accrual of up to \sim 20 evaluable subjects will be considered with the potential to stop accrual early if the boundary is crossed. Thus, accrual can be considered sufficient if the following n/N values are observed: 7/10, 8/11, 8/12, 9/13, 9/14, 10/15, 10/16, 11/17, 11/18, 12/19, 12/20. For all these values, the ORR is \geq 60% with a lower 1-sided binomial confidence bound of \geq 39%.

Experience indicates the rates of discontinuations from rituximab or atezolizumab therapy are < 5% (Genentech 2016, Genentech 2017). A rate of AE discontinuations of therapy due to adverse events of \geq 25% in the 2 combination therapy groups of LAM-002A/rituximab (N = 12) or LAM-002A/atezolizumab (N = 12) would suggest a potential adverse interaction among the components of the combination therapy. Sequential Pocock-type boundaries will be used to continuously monitor the rate of AE discontinuations and to test the null hypothesis, after each subject, that the event rate is \geq 0.25 using a 1-sided significance test of \sim 0.05. AE discontinuation rates will be considered excessive if the following n/N values are observed: -/1, -/2, 3/3, 3/4, 4/5, 4/6, 5/7, 5/8, 5/9, 6/10, 6/11, 7/12. With this method, the probability of detecting an AE discontinuation safety signal ranges from 0.091 to >0.820 for true discontinuation rates of 25% to \geq 60%. If excessive levels of AE discontinuation are observed, the sponsor, working in collaboration with the cooperating companies and investigators, will take appropriate actions (eg, continuation of the cohort with modifications in design or monitoring plan, interruption of cohort accrual, cohort therapy discontinuation).

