4.1.5. Overview of Indication

Non-Hodgkin's lymphoma (NHL) is a collective term for a heterogeneous group of lymphoproliferative malignancies with differing severities, ranging from slow growing to aggressive subtypes, and varying responses to treatment. In 2015, it is estimated that there will be 71,850 new cases of NHL and an estimated 19,790 people will die of this disease (National Cancer Institute SEER webpage). The two most common types, diffuse large B-cell lymphoma (DLBCL) and follicular lymphoma (FL), will account for about half of these (Martelli 2013). Other relatively common lymphomas include chronic lymphocytic leukemia/small lymphocytic lymphoma (CLL/SLL) (6%), mantle cell lymphoma (MCL, 6%),

and marginal zone lymphoma (MZL, 6%). DLBCL is further divided into two subtypes, "GCB" and "ABC" (also called "non-GCB"), based on resemblance to normal stages of B-cell development by gene expression profiling (Alizadeh 2000, Rosenwald 2002). The GCB (germinal center B-cell) type arises from malignant transformation of normal germinal center B-cells, and the ABC (activated B-cell) type arises from post-germinal center B-cells in the process of differentiating into plasma cells. ABC DLBCLs have an inferior prognosis compared to GCB DLBCLs, but several novel agents are in development with unique activity in ABC disease (Hans 2004, Cultrera 2012).

The median age at diagnosis of NHL is the seventh decade of life, though they can occur at any age. The prognosis of NHL depends on the histologic type, stage, and treatment.

Management of NHL varies widely depending upon histology. NHL patients are usually treated with chemotherapy, with or without radiation. Virtually all B-cell lymphomas are treated with chemotherapy in combination with the anti-CD20 monoclonal antibody rituximab (Zelenetz 2014). If NHL persists or recurs after standard treatment, autologous stem-cell transplantation (ASCT) may be a potentially curative option for patients with DLBCL (Raut 2014), though the cure rate for ASCT is low for patients relapsing after standard R-CHOP (rituximab, cyclophosphamide, doxorubicin, vincristine, and prednisone).

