6.1.2. Expansion Stage (Stage 2)

Once the MTD and/or recommended phase 2 dose (RP2D) and schedule is determined, the study will enter the expansion stage, in which cohorts of subjects will be accrued in order to obtain additional information on safety, tolerability, preliminary anti-tumor activity, PK, and pharmacodynamic data at the RP2D and schedule when LAM-002A is administered alone or in combination with rituximab/rituximab hyaluronidase or atezolizumab. Expansion-stage cohorts will comprise groups of subjects with specific types of previously treated, relapsed, progressive, and measurable NHL who will receive LAM-002A monotherapy or LAM-002A-containing combination therapy as shown in Table 2. For both monotherapy and combination cohorts, the starting dose of LAM-002A will be 125 mg BID administered continuously.

Version 9, 18 Feb 2020

Table 2: Expansion Stage Disease Types and Therapies

Cohort Number	NHL Type	Investigational Drug	Combination Drug	Evaluable Subjects, n
1	FL	LAM-002A		Up to ~20
2	MZL	LAM-002A		6
3	DLBCL-GCB	LAM-002A		6
4	DLBCL-ABC	LAM-002A		6
5	FL or MZL	LAM-002A	Rituximab or rituximab hyaluronidase human	Up to ∼20 with FL
6	DLBCL-GCB or DLBCL-ABC	LAM-002A	Rituximab or rituximab hyaluronidase human	6
7	FL or MZL	LAM-002A	Atezolizumab	6
8	DLBCL-GCB or DLBCL-ABC	LAM-002A	Atezolizumab	6

Abbreviations: ABC: activated B-cell (subtype); DLBCL: diffuse large B-cell lymphoma; FL: follicular lymphoma; GCB: germinal center B-cell (subtype); MZL: marginal zone lymphoma; NHL: non-Hodgkin lymphoma

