6.1.4. Subject Allocation (Stage 1 and Stage 2)

Subjects will be allocated to the cohorts by the study sponsor working in collaboration with each investigator considering the availability of openings for enrollment in Stage 1 or 2, disease type (i.e., FL, MZL, DLBCL-GCB, DLBCL-ABC, or other indications), therapy history (e.g., prior use of anti-CD20 or anti-PD1/PDL1 antibodies), and current disease status (e.g., potential to benefit from rituximab treatment based on past responses to anti-CD20 antibody therapy).

During Stage 1 dose ranging with LAM-002A monotherapy, allocation will be performed according to a 3+3 dose-escalation procedure with the requirement that each cohort of 3 subjects be observed for ≥4 weeks before another cohort is enrolled (as detailed in Section 6.6). During Stage 2 cohort expansion evaluating LAM-002A monotherapy, allocation will be performed as subjects present to the accruing clinics and there will be no specific restrictions on the cadence of enrollment. During Stage 2 cohort-expansion of LAM-002A combinations with rituximab and

Version 9, 18 Feb 2020

atezolizumab, enrollment of the first 3 subjects in each combination cohort will be restricted such that each subject must be enrolled sequentially and observed for \geq 3 weeks before the next subject is enrolled. Beginning with the 4th patient in each combination group, further enrollment may proceed without restriction as long as the continuous reassessment boundaries for toxic drug discontinuations are not met (as detailed in Section 6.8.4.4 and Section 14.1.2).

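### The 0/6 exclusion statement holds for the single-type cohorts 2 to 4, but not per lymphoma type in the six-subject cohorts that mix types (clearly cohort 7; cohorts 6 and 8 if GCB and ABC count separately)

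*Combined protocol and SAP*

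**What the plan says.** Section 14.1.2 states that "expansion cohorts of 6 subjects will be accrued". It sets the level of interest per indication: an ORR of at least "35% is considered of potential interest in each of the selected indications". The triggering result is counted per cohort: "If 0/6 subjects in a cohort experience an objective response", a population ORR at or above that level "for that cancer can be excluded with > 90% certainty (1-sided exact binomial 90% CI upper bound = 32"%). The synopsis repeats the statement, with at least six subjects per cohort.

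Table 2 in Section 6.1.2 (Table S-2 in the synopsis) defines the cohorts. Cohorts 2, 3 and 4 (monotherapy) each enrol one type, MZL, DLBCL-GCB and DLBCL-ABC respectively, with six evaluable subjects. Cohorts 6 and 8 (with rituximab and atezolizumab respectively) enrol "DLBCL-GCB or DLBCL-ABC", and cohort 7 (with atezolizumab) enrols FL or MZL. Each of these three also has six evaluable subjects in total, with no minimum per type. Cohort 5 also admits FL or MZL, but its target of about 20 is counted in FL subjects.

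Section 6.1.4 allocates subjects by "disease type (i.e., FL, MZL, DLBCL-GCB, DLBCL-ABC, or other indications"). Section 14.9 estimates the ORR for each cohort and mentions no estimate by type within a cohort.

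**The concern.** The count is per cohort and the conclusion is per cancer. The two coincide when a cohort holds one type. When it holds two, no response among six subjects tells us about one type only through the subjects who had that type, unless the types are assumed to share one ORR. The plan states no such assumption, and it keeps the four types apart in cohorts 1 to 4 and in Section 6.1.4.

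At stake is how a null result in a pooled combination cohort would be read. Section 14.1.2 says these cohorts are meant to show whether activity is sufficient to justify further development in the selected tumour types. A report that cites the stated certainty for MZL with atezolizumab, for example, could attach more than 90% to a conclusion resting on one or two MZL subjects.

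**Working it through.** **Inputs.** Cohort size 6, result 0 responders, ORR to be excluded 35%, 1-sided 90% exact binomial bound (all Section 14.1.2); types per cohort (Table 2). The split of types within cohorts 6 to 8 is not given, so every split from 1+5 to 5+1 is shown.

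**Formulas.** For 0 responders among n subjects with a common ORR:

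- 1-sided 90% exact upper bound = 1 − 0.10^(1/n)
- probability of 0/n at an ORR of 35% = 0.65^n
- certainty of excluding 35% or more = 1 − 0.65^n

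**Step 1: reproduce the plan's figure.** With n = 6, the bound is 1 − 0.10^(1/6) = 0.3187, or 32%. The probability of 0/6 at 35% is 0.65^6 = 0.0754, so the certainty is 0.9246. Both match the plan. The upper limit of a two-sided 90% interval would be 39.3%, so the 1-sided description is also correct.

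**Step 2: one type within a mixed cohort.** If k of the six subjects have a given type and none responds, only those k bear on that type:

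| k of 6 | Probability of 0/k at ORR 35% | Certainty of excluding 35% or more | 1-sided 90% upper bound |
|---|---|---|---|
| 6 | 7.5% | 92.5% | 31.9% |
| 5 | 11.6% | 88.4% | 36.9% |
| 4 | 17.9% | 82.1% | 43.8% |
| 3 | 27.5% | 72.5% | 53.6% |
| 2 | 42.3% | 57.8% | 68.4% |
| 1 | 65.0% | 35.0% | 90.0% |

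No split with both types present reaches 90% for either type. Even the larger type in a 5+1 split has a bound above 35%.

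**Step 3: what 0/6 does support in a mixed cohort.** For a fixed split, the probability of 0/6 is the product of the six individual non-response probabilities. That product cannot exceed (1 − average ORR)^6. The 32% bound is therefore valid for the average ORR of the enrolled mix. It also holds for each type if the types share one ORR.

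**Step 4: dependence on the other type.** Take a 3+3 split with one type at a true ORR of 35%. The probability of 0/6 is 0.65³ × (1 − p)³, where p is the other type's ORR:

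- p = 0: 27.5%
- p = 10%: 20.0%
- p = 20%: 14.1%
- p = 35%: 7.5%

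It falls to 10% or less only when p is at least about 28.6%. These ORRs and the 3+3 split are assumptions for illustration.

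**The case against.** Several points on the other side stand.

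- **There is no futility rule.** A reader might infer that a sponsor following the text would drop an indication wrongly 27.5% of the time against a nominal 10%. The documents do not support that. The statement sits under the sample-size heading and attaches no action to 0/6. Where the plan wants a boundary, Section 14.1.2 writes one: response counts for FL accrual, and discontinuation counts with listed actions. Section 14.9 plans a two-sided 95% exact interval per cohort, not a 1-sided test. The 27.5% also needs a 3+3 split with true ORRs of 35% and 0%.
- **Cohorts 6 and 8 are open to reading.** Eligibility lists DLBCL as one diagnosis, and Section 4.1.5 says that "DLBCL is further divided into two subtypes". If the cancer meant is DLBCL, the bound describes the enrolled DLBCL mix. Table 2 and Section 6.1.4 support the other reading. The remark in Section 4.1.5 that "several novel agents are in development with unique activity in ABC disease" concerns other agents and does not show that sensitivity to LAM-002A differs by subtype.
- **In cohort 7 the 0/6 case may already be moot.** Section 4.1.4.2 reports nine FL responders across monotherapy and both combinations, without counts per regimen. On a natural reading at least one received atezolizumab. The wording would still be wrong for a cohort mixing FL and MZL.
- **The plan leaves room for more precision.** Section 6.2 allows accrual above the roughly 76 planned, partly to tighten efficacy bounds. The synopsis foresees analyses by tumour characteristics, and Section 14.2 defers detail to an SAP. Only the first part of the combined document was examined, so by-type reporting elsewhere cannot be ruled out.

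These points limit the consequence. They do not make the per-cancer statement true for a mixed cohort.

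**Conclusion.** The statement is correct for cohorts 2 to 4. It does not hold per type in cohort 7 when both FL and MZL are enrolled. The same applies to cohorts 6 and 8 if GCB and ABC are treated as separate types, as the plan does elsewhere. In those cohorts the certainty for one type lies between 35.0% and 88.4% and the bound between 36.9% and 90.0%, depending on the split. The stated figures would apply to a single type only if all six subjects had it, or under an assumption of a common ORR that the text examined does not state.

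This is an error in the scope of a stated inference. The binomial calculation is sound, and no sample size, boundary or planned estimate changes.

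**What to change.** In Section 14.1.2 and the synopsis:

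1. Limit the per-cancer statement with its 32% bound to cohorts 2 to 4.
2. State that in cohorts 6 to 8 no response among six excludes an ORR of 35% or more for the enrolled mixture only.

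In the analysis plan, add responders/N by type within the pooled cohorts (FL and MZL; GCB and ABC), with exact bounds, including the 1-sided 90% bound so that it matches the rationale. Histology is an eligibility item (Section 7.1) and DLBCL subtype is evaluated at baseline (Section 8.1.5), so no new data or subjects are needed.

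Do not add a rule that a type is dropped only after 0 of 6 of that type. The plan has no such rule, and a six-subject cohort containing both types could never meet it.

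The cost is two sentences, one extra table split and a less favourable stated certainty for the mixed cohorts. The by-type bounds will be wide and should be presented as descriptive.

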Based on historical data with other treatments, it is known that an ORR of < 20% in subjects with relapsed FL receiving LAM-002A monotherapy would be uninteresting while achieving a target ORR of \geq 40% would suggest that further development is warranted. Sequential boundaries will be used to continuously monitor that the ORR is \geq 40% while excluding an ORR of < 20% using a 1-sided test with a significance level of 0.05. A significant result with this testing would conclude with 95% confidence that the actual ORR is \geq 20%. Accrual of up to \sim 20 evaluable subjects will be considered with the potential to stop accrual early if the boundary is crossed. Thus, accrual can be considered sufficient if the following n/N values are observed: 4/5, 4/6, 4/7, 5/8, 5/9, 5/10, 5/11, 6/11, 6/12, 6/13, 6/14, 7/15, 7/16, 7/17, 8/18, 8/19, 8/20. For all these values, the ORR is \geq 40% with a lower 1-sided binomial confidence bound of \geq 20%.

As noted above, the target ORR with LAM-002A alone is ~40%. Adding rituximab or rituximab hyaluronidase human to LAM-002A would be expected to enhance the ORR over that associated with single-agent LAM-002A. Thus, the combination of LAM-002A/rituximab could warrant further development if an ORR of \geq 60% could be targeted in preference to an ORR of < 40%. Accordingly, for combination therapy, sequential boundaries will be used to continuously monitor that the ORR is \geq 60% while excluding an ORR of 39% using a 1-sided test with a significance level of 0.05. A significant result with this testing would conclude with 95% confidence that the actual ORR is > 39%.

Protocol: LAM-002A-NHL-CLN01

Version 9, 18 Feb 2020

Accrual of up to ~20 evaluable subjects will be considered with the potential to stop accrual early if the boundary is crossed. Thus, accrual can be considered sufficient if the following n/N values are observed: 7/10, 8/11, 8/12, 9/13, 9/14, 10/15, 10/16, 11/17, 11/18, 12/19, 12/20. For all these values, the ORR is $\geq 60\%$ with a lower 1-sided binomial confidence bound of $\geq 39\%$.

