14.9. Efficacy Analysis

The tumor response will be assessed by the modified criteria for NHL (Cheson 2014) and revised guidelines for the diagnosis and treatment of CLL (Hallek 2008, Cheson 2012) (see Appendix 2).

The objective response rate will be estimated for each dose escalation cohort and each expanded cohort. The estimate of the objective response rate will be calculated based on the maximum likelihood estimator (i.e., crude proportion of subjects whose best overall response is CR or partial remission [PR]). The estimate of the objective response rate will be accompanied by 2-sided 95% exact binomial confidence intervals.

The duration of objective response will be calculated for subjects who achieve CR or PR. For such subjects, the duration of objective response is defined as the number of days from the start date of PR or CR (whichever response is achieved first) to the first date that progressive disease is objectively documented. The duration of objective response will be right-censored for subjects who achieve CR or PR and meet 1 of the following conditions: 1) non-protocol anticancer treatment started before documentation of disease progression, 2) death or documented disease progression after more than 1 missed disease assessment visit, or 3) alive and does not have documentation of disease progression before a data analysis cutoff date.

The duration of objective response will be summarized descriptively using the Kaplan-Meier method. The 50th percentile of the Kaplan-Meier distribution will be used to estimate the median response duration.

Progression-free survival (PFS) will be measured as from the date of enrollment to the date of documented progression or death (whatever the cause). Subjects who are alive and progression free at last follow-up (up to a year from first treatment at Cycle 1 day 1) will be censored. Those who start another anticancer treatment without evidence of progression will be censored at start date of the new therapy.

The PFS will be summarized descriptively using the Kaplan-Meier method. The 50th percentile of the Kaplan-Meier distribution will be used to estimate the median PFS of each cohort of subjects.

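### The follicular lymphoma response boundaries are unadjusted fixed-N limits, so the stated 1-sided 0.05 becomes about 8–9% (monotherapy) and 10% (rituximab combination) if every subject is a look

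*Combined protocol and SAP*

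**What the plan says.** Section 14.1.2, repeated in the synopsis, opens the rule for FL monotherapy with "Sequential boundaries will be used to continuously monitor that the ORR is" at least 40%, and continues with "excluding an ORR of < 20% using a 1-sided test with a significance level of 0.05". A significant result is said to give 95% confidence that the true overall response rate (ORR) is at least 20%. Up to about 20 evaluable subjects may be accrued, and accrual may end early on a crossing. Seventeen n/N values are listed for N = 5 to 20. The middle of the list reads "5/8, 5/9, 5/10, 5/11, 6/11, 6/12, 6/13, 6/14", so N = 11 appears twice. Every value is said to have a 1-sided lower binomial bound of at least 20%.

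The rituximab combination has the same structure, "while excluding an ORR of 39% using a 1-sided test with a significance level of 0.05", with eleven values from 7/10 to 12/20, each said to have a lower bound of at least 39%.

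For the final analysis, Section 14.9 states: "The estimate of the objective response rate will be calculated based on the maximum likelihood estimator", that is, the crude proportion, with a 2-sided 95% exact interval.

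**The concern.** A continuously monitored rule with a stated significance level should have that level over the whole sequence of looks. Here the only justification offered is a confidence bound at each N taken alone, and no repeated-look adjustment is described. If the bounds are unadjusted, the chance that a regimen with an uninteresting response rate crosses at some point is larger than 0.05, and the 95% confidence statement attached to a crossing is not correct. Section 14.1.2 ties these thresholds to whether further development is warranted, so a reader of the results would rely on the stated level. Stopping on a high count also pushes the crude response rate upward, and Section 14.9 does not mention this.

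**Working it through.** **Inputs (Section 14.1.2).** Null ORR p0 = 0.20 (monotherapy) and 0.39 (combination); targets 0.40 and 0.60; 1-sided 0.05; maximum N = 20; the two printed lists.

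**Step 1: reproduce the 0.05.** For a listed count b at size N, the fixed-sample tail is P(X ≥ b | N, p0), with X binomial.

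- 4/5: 5 × 0.2⁴ × 0.8 + 0.2⁵ = 0.0067
- 4/7: 0.0333
- 8/20: 0.0321
- 5/11: 1 − (0.0859 + 0.2362 + 0.2953 + 0.2215 + 0.1107) = 0.0504; exact 1-sided 95% lower bound 19.96%
- 6/11: 0.0117; lower bound 27.1%
- 7/10, 8/12, 9/14, 10/16 at 39%: 0.0477, 0.0493, 0.0497, 0.0491
- 12/20 at 39%: 0.0466

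Every entry except 5/11 is the smallest count whose fixed-sample tail is at most 0.05. So the stated 0.05 is reproduced as a separate limit at each N, with nothing held back for repeated looks.

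**Step 2: overall error.** Let f(N, s) be the probability of s responses among N with no earlier crossing, and b(N) the boundary. Then f(N, s) = (1 − p) f(N−1, s) + p f(N−1, s−1). At each listed N the mass with s ≥ b(N) is removed and counted as a crossing. The overall error is the sum of the removed mass at p = p0.

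As a check, the same recursion applied to the AE-discontinuation boundaries in Section 14.1.2 gives 0.0908 at 25% and 0.8201 at 60%. The plan prints 0.091 and 0.820.

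| N of first crossing | Monotherapy at 20%, 5/11 in force | Monotherapy at 20%, 6/11 in force |
|---|---|---|
| 5, 6, 7 | 0.0067, 0.0102, 0.0164 | the same |
| 9, 10 | 0.0046, 0.0095 | the same |
| 11, 12 | 0.0147, 0 | 0, 0.0029 |
| 13, 14 | 0.0040, 0.0081 | 0.0063, 0.0100 |
| 16, 17 | 0.0025, 0.0053 | 0.0028, 0.0058 |
| 19, 20 | 0.0017, 0.0036 | 0.0018, 0.0038 |
| **Total** | **0.0873** | **0.0809** |

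Combination at 39%: N = 10, 12, 14, 16, 18, 20 contribute 0.0477, 0.0156, 0.0118, 0.0095, 0.0078 and 0.0065, total **0.0990** (last digit from unrounded terms). At a true 40% the total is 0.1144. The first combination look alone uses 0.0477, so adding the N = 12 look already gives 0.0477 + 0.0156 = 0.0633.

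**Step 3: fewer looks (illustrative schedules, not in the plan).**

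| Looks at N | Monotherapy at 20% | Combination at 39% |
|---|---|---|
| 20 only | 3.2% | 4.7% |
| 10, 20 | 5.2% | 7.5% |
| 12, 16, 20 | 4.5% | 8.2% |
| 10, 15, 20 | 5.4% | 7.8% |

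**Step 4: the crude rate.** Averaging s/N over all end points of the same recursion (first crossing, or N = 20) gives 46.8% at a true 40% for monotherapy and 63.4% at a true 60% for the combination.

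**The case against.** The best defence is about weight. The primary objective is the MTD and the primary endpoint is DLT frequency (Sections 5.1 and 5.4); antitumor activity is secondary and preliminary. A crossing only permits accrual to be judged sufficient and binds no one. That stands, and it sets the severity. It does not rescue the figure, because the 0.05 and the 95% confidence are attached to any crossing.

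The size also depends on the looks. Section 6.1.4 places no cadence limit on monotherapy enrolment, and the first on-treatment scan falls around Cycle 3 Day 1, so reviews could be batched. Some sparse schedules bring monotherapy to about 5% or below. The multi-look combination schedules above all stay above 5%. The plan's wording and its lists, however, describe a look after each subject.

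Section 14.9 gives partial protection. The 2-sided 95% interval has a stricter lower limit: 19.1% at 8/20, 18.7% at 5/10, 18.4% at 4/7, and about 36% at 12/20, none of which excludes the null. Section 14.3.1 also counts nonevaluable subjects as failures in the full analysis set. Neither provision corrects the stated level.

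Stronger readings are tempting but not supported:

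- A reader might treat each entry as its own 5% test. The tails run from 0.007 to 0.050, and only 12 of the 16 monotherapy sample sizes can be a first crossing.
- A reader might take 5/11 as a material error. It misses 20% only in the second decimal and reads as a rounding or typing slip.
- A reader might cite the unbiased estimate at 8/20, 28.6% against a crude 40%, as typical. It is the most extreme boundary point; at 4/5 crude and unbiased estimates are both 80%.
- A reader might infer that the boundaries must be replaced. New lists would barely change the bias (46.4% against 46.8% at a true 40%).

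Finally, Section 14.2 lets the SAP modify these plans, and only the first of the two parts of the combined document was examined. An adjustment elsewhere cannot be ruled out, although the printed counts themselves contain none.

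**Conclusion.** The stated level is wrong as written. With a look at every listed N, independent subjects and a stop at first crossing, the overall 1-sided error is about 8–9% for monotherapy at 20% (8.1% with 6/11, 8.7% with 5/11) and 9.9% for the combination at 39%. That is 1.6 to 2.0 times the stated 0.05. The 95% confidence statements hold only for a single look at an N fixed in advance. The arithmetic is certain for the printed lists; the realised inflation depends on how many looks are taken. This is a should-fix labelling fault in a secondary, preliminary assessment. It does not invalidate the FL cohorts or the trial's primary objective.

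**What to change.** In Section 14.1.2 and the synopsis:

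1. Delete 5/11, leaving 6/11 as the only value at N = 11.
2. Replace the significance-level and 95% confidence sentences with wording such as: *Each listed count is the smallest whose one-sided 95% exact lower bound reaches 20% (monotherapy) or 39% (combination) at that N taken alone. The bounds are not adjusted for repeated looks. If every evaluable subject from the first listed N is a look, the overall one-sided error is about 0.081 at 20% and 0.099 at 39%.*
3. In Section 14.9, add that after a boundary stop the crude ORR and its exact interval ignore the stopping rule, with the averages of 46.8% at a true 40% and 63.4% at a true 60% as a guide.

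This changes text only. Dropping 5/11 lowers the chance of crossing at a true 40% from 68.7% to 67.9%.

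Replacing the lists to hold 0.05 is optional. A constant nominal level of about 0.0265 (ending at 9/20) gives an overall error of 4.9% for monotherapy; about 0.0285 (ending at 13/20) gives 4.7% for the combination. The chance of crossing then falls from 69% to 58% at a true 40% and from 68% to 53% at a true 60%. Mean sample size rises from 13.2 to 14.7 and from 14.7 to 16.2. Because FL responses had already been observed when these boundaries were justified, new lists could also look like a post hoc change. Restating the error avoids that.

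### The monotherapy FL boundary lists both 5/11 and 6/11, and 5/11 falls just short of the plan's own criterion of a lower bound of at least 20%

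*Combined protocol and SAP*

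**What the plan says.** Section 14.1.2 sets a sequential rule for up to about 20 evaluable subjects with relapsed FL on LAM-002A alone. The aim is a response rate of at least 40% while "excluding an ORR of < 20% using a 1-sided test with a significance level of 0.05". A crossing is to be read as a confidence statement: "A significant result with this testing would conclude with 95% confidence that the actual ORR is" at least 20%.

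Accrual can be considered sufficient at any of 17 responder/subject pairs: "4/5, 4/6, 4/7, 5/8, 5/9, 5/10, 5/11, 6/11, 6/12, 6/13, 6/14, 7/15, 7/16, 7/17, 8/18, 8/19, 8/20". The paragraph closes with a claim about the whole list. It begins "For all these values, the ORR is" at least 40% and goes on "with a lower 1-sided binomial confidence bound of" at least 20%.

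The Synopsis, under the basis for the expansion-stage sample sizes, prints the same list with the same pair of entries: "5/8, 5/9, 5/10, 5/11, 6/11, 6/12". The two places agree with each other, so this is not a copying difference between them.

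**The concern.** A sequential boundary needs one minimum number of responders for each number of subjects. Every N from 5 to 20 has one entry, except N = 11, which has two. The rituximab-combination boundary and the AE-discontinuation boundary in the same section have no such duplicate.

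If entries are read as minimums, as everywhere else in the list, 5/11 says that accrual may stop and 6/11 says that it should continue at 5 responders. If the list is read simply as a set of sufficient results, accrual may stop at 5/11. It then matters whether 5/11 meets the criterion claimed for every entry. If it does not, the plan permits a claim of 95% confidence that the rate is at least 20% on a result that does not support it. With both entries printed, the choice between them could be made after the data are seen.

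**Working it through.** **Inputs, all from Section 14.1.2.** Null response rate p0 = 0.20; one-sided level 0.05; observed rate at least 0.40; lower one-sided bound at least 0.20; the 17 listed pairs.

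**Method.** The plan calls the bound only binomial, but the same section uses an exact binomial bound for its 0/6 rule. As a check on that method, the exact 90% upper bound for 0/6 is 1 − 0.10^(1/6) = 0.319, which reproduces the stated 32%. The exact one-sided 95% lower bound for x responders in n is the 0.05 quantile of a Beta(x, n − x + 1) distribution. It reaches 0.20 exactly when P(X ≥ x | n, 0.20) ≤ 0.05.

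**The tail for 5/11 by hand.**

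- P(X = 5) = 462 × 0.2^5 × 0.8^6 = 0.03876
- P(X = 6) = 462 × 0.2^6 × 0.8^5 = 0.00969
- P(X = 7) = 330 × 0.2^7 × 0.8^4 = 0.00173
- P(X ≥ 8) = 0.00024
- Sum: P(X ≥ 5) = 0.0504, above 0.05
- For 6/11, leaving out the first term: 0.00969 + 0.00173 + 0.00024 = 0.0117, below 0.05

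**All listed pairs.**

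| Pair | Observed | Exact lower bound | Tail at 20% |
|---|---|---|---|
| 4/5 | 80.0% | 34.26% | 0.0067 |
| 4/6 | 66.7% | 27.13% | 0.0170 |
| 4/7 | 57.1% | 22.53% | 0.0333 |
| 5/8 | 62.5% | 28.92% | 0.0104 |
| 5/9 | 55.6% | 25.14% | 0.0196 |
| 5/10 | 50.0% | 22.24% | 0.0328 |
| **5/11** | **45.5%** | **19.96%** | **0.0504** |
| 6/11 | 54.5% | 27.12% | 0.0117 |
| 6/12 | 50.0% | 24.53% | 0.0194 |
| 6/13 | 46.2% | 22.40% | 0.0300 |
| 6/14 | 42.9% | 20.61% | 0.0439 |
| 7/15 | 46.7% | 24.37% | 0.0181 |
| 7/16 | 43.8% | 22.67% | 0.0267 |
| 7/17 | 41.2% | 21.19% | 0.0377 |
| 8/18 | 44.4% | 24.40% | 0.0163 |
| 8/19 | 42.1% | 22.97% | 0.0233 |
| 8/20 | 40.0% | 21.71% | 0.0321 |

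Only 5/11 fails. With it removed, the exact rule plus the 40% condition gives the printed number as the minimum at all 16 values of N from 5 to 20.

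**Would another interval rescue 5/11?** Its lower bound would be 24.2% by Wilson, 20.8% by Wilson with continuity correction, 23.5% by Jeffreys, 22.5% by mid-p, 20.8% by Wald, and 24.1% by an exact 90% bound. Each of these would also admit lower thresholds elsewhere, such as 3/5 and 4/8, so none produces the printed list.

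**Practical size.** I assumed a look after every subject from N = 5 to N = 20.

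| True response rate | Reach 5/11 with no earlier crossing | Ever cross, 5/11 kept | Ever cross, 5/11 removed |
|---|---|---|---|
| 20% | 0.015 | 0.087 | 0.081 |
| 40% | 0.084 | 0.687 | 0.679 |

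Under such looks, a cohort still open at N = 11 had at most 4/10 before and so has at most 5/11. The 5/11 entry is therefore the only one that can trigger a first crossing at that N.

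**The case against.** Three points can be made for leaving the list alone or for treating this as trivial.

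First, rounding. The section states its bounds as whole percents, and 19.96% rounds to 20%. With whole-percent rounding every listed pair satisfies the closing sentence and no other threshold moves: the only other near miss, 7/18 with a bound of 19.9%, fails the 40% condition at 38.9%. On that reading 5/11 is the boundary and 6/11 is the surplus entry. Rounding is a plausible origin of the slip, but it does not save the text. The list would still carry an entry to remove, and 0.0504 still exceeds the stated 0.05. The companion combination list meets its 39% bound without rounding: its tightest pair, 9/14, has a bound of 39.04% and a tail of 0.0497.

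Second, the wording is permissive and presents a list of sufficient results, so nothing explicitly says to continue at 5/11. This is fair as a literal reading. It means that the plan allows stopping at a result that fails its own criterion.

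Third, the effect is small. The miss is 0.04 percentage points and concerns one result in one expansion cohort. The primary endpoint (DLT frequency) is untouched, as are the two-sided 95% exact intervals that Section 14.9 plans for the response rate. Nor does removing 5/11 control the sequential error rate, because each bound is a fixed-N bound applied at repeated looks. All of this stands. It limits the importance of the point but does not remove the error.

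**Conclusion.** The concern holds. N = 11 carries two thresholds, and 5/11 does not meet the criterion that the plan claims for every entry: a lower bound of 19.96% against 20%, and a tail of 0.0504 against 0.05. The 16 other pairs meet it. The conclusion assumes the exact binomial bound, which the plan does not name for this rule. It is the only method tried that reproduces the rest of the list, and the section uses it for the 0/6 rule.

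The consequence is confined to a cohort that stands at exactly 5 of 11. With a look after every subject, that has probability about 0.084 at the 40% target, roughly 1 cohort in 12, and 0.015 at 20%. It is worth correcting because it is a decision threshold, not because it changes the operating characteristics much.

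**What to change.** Delete 5/11 from the monotherapy list in Section 14.1.2 and in the Synopsis, leaving 6/11 as the only entry at N = 11. State in both places that the bound is the exact (Clopper-Pearson) one-sided 95% bound, compared with 20% without rounding. The closing sentence about all listed values then becomes true.

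The cost is one entry removed and a few words added in two places; no other threshold and no sample size changes. The edit should not be described as restoring an overall 0.05 level. With a look after every subject, the chance of ever crossing at a true rate of 20% remains 0.081.
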